4.4 Discontinuation/Withdrawal of Study Participants

The Informed Consent will require that subjects allow follow-up for the primary outcome and safety through to 56 days post-enrollment or death. A subject may withdraw from the study by withdrawing consent to continue participation. If a subject withdraws consent from participating in the study at any time after enrollment, but prior to the final scheduled study visit, the investigator will make every effort to have the participant complete all assessments at the time of withdrawal. All data collected up to the time of withdrawal will be used for data analyses. The request to withdraw consent must be documented.

Discontinuing treatment is not a reason for withdrawing from participating in the study. Subjects who discontinue treatment for any reason should be followed until 56 days postenrollment or death, whichever comes first.

Reasons for treatment discontinuation are defined below.

- The PI or Medical Monitor consider that continuation of treatment may pose a safety risk to the subject. Treatment discontinuation will be considered a treatment failure, unless the subject discontinues treatment due to pregnancy or renal insufficiency. The subject should however continue to be monitored as per protocol for outcome measures through to study end (Day 56).
- Adverse event (Adverse Reaction): clinical or laboratory events that in the medical judgement of the investigator are grounds for discontinuation of treatment. This will be considered as a treatment failure. Subjects should however continue to be monitored as per protocol for outcome measures through to study end (Day 56).
- Lost to follow-up: for subjects who are discharged from the hospital within 28 days of treatment initiation who cannot be contacted after multiple attempts, will be

considered as Lost to Follow-up for purposes of Long-term outcomes (56 days). Otherwise, without relapse of COVID-19 symptoms, discharge within 28 days of enrollment is considered a treatment success. For subjects who are discharged from the hospital, every effort should be made to contact the subject to determine clinical status and adverse events post-discharge.

• Transfer of subject to another hospital. All transfers will be considered treatment failures.

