5.4 Dispensing of Study Drug

Pharmacy service will provide 3 capsules per day (GLS-1027 or matching placebo) based on randomization assignment. The randomization treatment code will be provided to the site pharmacists from a web-based system. How to access the randomization system is covered in a separate Pharmacy Manual. It is the responsibility of the Investigators that study drug is dispensed only to study participants by hospital nursing personnel. Authorized personnel are the only ones to dispense product according to local regulation and study specific Delegation Log. Study drug administration is to be discontinued for periods when subject either has an eGFR < 60 mL/min/1.73 m², is unable to take medications orally, or reaches a study endpoint (WHO COVID-19 classification of 6 or greater).

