3. STUDY DESIGN AND PLAN

This is a Phase II, randomized, double-blind, placebo-controlled study to assess 2 dose levels of GLS-1027 for the prevention of treatment failure among participants admitted to the hospital with PCR confirmed infection with SARS-CoV-2 (WHO classification 3 or 4). Subjects can be enrolled up to 72 hours from the time of hospital admission.

Participants will be randomized to placebo or GLS-1027 at either 120 mg or 360 mg daily in a 1:1:1 ratio as adjunctive to standard of care based on the hospital COVID-19 treatment algorithm and/or local COVID-19 treatment practices. Participants will be administered study drug for a maximum treatment period of 14 days or until discharge or death, whichever comes first. Primary outcome will be assessment at day 28, with follow-up to continue to Day 56 to document AEs and outcome as to discharge, death, or WHO COVID-19 classification level if subject remains hospitalized.

All subjects will be considered to have completed the study except for the following circumstances:

- Withdrawal of consent from study
- Loss to follow-up
- Stopped study treatment for any reason other than discharge, pregnancy, or decreased renal function

Table 1: Schedule of Assessments

Tests and Observations	1	2	3	4	5	6	7	8	9	10	11	12	13	14	15	28	56 ^m
Clinical Evaluations																	
Obtain written Informed Consent	Х																
Confirm Eligibility Criteria	Х																
Demographics	Х																
Medical History	Х																
Concomitant Medications	Х	Х	Х	Х	Х	Х	Х	Х	Х	Х	Х	Х	Х	Х	Х	Х	Х
Review Medical Record	Х	Х	Х	Х	Х	Х	Х	Х	Х	Х	Х	Х	Х	Х	Х	Х	Х
WHO COVID-19 Classification (Appendix B)	Х	Х	Х	Х	Х	Х	Х	Х	Х	Х	Х	Х	Х	Х	Х	Х	Х
Safety Evaluations																	
Record Adverse Events	Х	Х	Х	Х	Х	Х	Х	Х	Х	Х	Х	Х	Х	Х	Х	Х	Х
Record AM Vital Signs a	Х	Х	X	Х	Х	Х	Х	Х	Х	Х	Х	Х	Х	Х	Х		
Record Hematology ^b	Х	Х	Х			Х			Х			Х			Х		
Record Basic Metabolic Panel ^c	Х	Х	Х	Х	Х	Х	Х	Х	Х	Х	Х	Х	Х	Х	Х		
Record liver function studies (LFTs) °	Х					Х			Х			Х			Х		
Record other labs ^d (for days available)	Х	Х	Х	Х	Х	Х	Х	Х	Х	Х	Х	Х	Х	Х	Х		
Record Procalcitonin (baseline value) e	Х																
Record admission CXR	Х																
Record if care given in ICU setting	Х	Х	Х	Х	Х	Х	Х	Х	Х	Х	Х	Х	Х	Х	Х		
Record whether nasal O ₂ prescribed and dose level (L/min) ^f	Х	Х	Х	Х	Х	Х	Х	Х	Х	Х	Х	Х	Х	Х	Х		
Record whether CPAP prescribed and expiratory pressure ⁹	X	X	X	X	Х	Х	X	Х	Х	X	Х	Х	X	Х	X		

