7. STUDY POPULATION

7.1. Subject Disposition

The number and percentage of subjects who were screened and failed screening, who were in each analysis population, who completed the study and who discontinued prior to study completion will be presented by treatment group (GLS-1027 120 mg, GLS-1027 360 mg, and placebo) and overall. Subjects who discontinued prior to completing the study will also be summarized by reason for discontinuation.

Subject disposition will also be listed.

CONFIDENTIAL Page 9 03DEC2021

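### SAP 3 treats most treatment stops as study non-completion, so subjects with complete follow-up can be reported as having discontinued the study

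*SAP*

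**What the plan says.** SAP 3 starts from a general rule, "All subjects will be considered to have completed the study except for the following circumstances", and lists three exceptions: withdrawal of consent, loss to follow-up, and having "Stopped study treatment for any reason other than discharge, pregnancy, or decreased renal function". The same section sets out how dosing ends: "Participants will be administered study drug for a maximum treatment period of 14 days or until discharge or death, whichever comes first".

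SAP 7.1 presents completers and non-completers by treatment group and adds that "Subjects who discontinued prior to completing the study will also be summarized by reason for discontinuation". Table 14.1.1.1 has the rows Completed the study and Discontinued the study, with placeholder reason rows beneath. It has no row for completion of treatment.

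Protocol 4.4 keeps the two ideas apart: "Discontinuing treatment is not a reason for withdrawing from participating in the study". Subjects who stop drug for any reason "should be followed until 56 days postenrollment or death, whichever comes first". SAP 6.4, which defines the per-protocol set, regards a subject as having completed the trial by meeting the treatment-failure endpoint or by being discharged within 14 days without meeting it.

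**The concern.** A disposition table is where a reader looks to see how many randomised subjects left the study and how much outcome data may be missing. The third exception in SAP 3 turns a fact about dosing into a statement about study participation. It also closely matches the treatment-discontinuation component of the primary endpoint, so the completion flag is built partly from endpoint events.

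Subjects whose Day 28 outcome is known, and who never left the study in the protocol's sense, would share a row with subjects who really did leave. If the drug reduces failures that end dosing, that row would also tend to differ between arms for reasons unrelated to attrition.

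**Working it through.** The plan gives no figure on this point, so there is nothing to reproduce. The check applies the SAP 3 rule to each way dosing can end and compares the result with protocol 4.4, 5.4 and 7.3.2 and SAP 6.4 and 8.1.

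1. **Permanent stop for an adverse event, followed to Day 56.** Protocol 4.4 allows this for "clinical or laboratory events that in the medical judgement of the investigator are grounds for discontinuation of treatment" and keeps the subject under observation to Day 56. An adverse event is not among the SAP 3 exemptions, so the subject is a non-completer. Under SAP 8.1 the same stop is a treatment failure, so under SAP 6.4 the subject has completed the trial. The conflict is clear.

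2. **Death on treatment.** SAP 3 names death as a planned end of dosing but does not exempt it, so the subject is a non-completer. Under protocol 4.4 follow-up properly ends at death. Death is WHO level 8, so the endpoint is met and SAP 6.4 counts the subject as completing the trial. The conflict holds, although such a subject is not followed to Day 56.

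3. **Intubation.** Protocol 5.4 suspends dosing for the period during which level 6 or above applies. Protocol 7.3.2 lists intubation among temporary halts, with restart after extubation once oral dosing is possible. If drug is never restarted, SAP 3 makes the subject a non-completer while SAP 6.4 makes the subject a completer. If drug is restarted, SAP 3 does not say whether the halt counts as having stopped. SAP 8.1 excepts temporary halts, but only for the endpoint.

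4. **Full 14-day course, still in hospital.** End of course is missing from the SAP 3 exemptions, so on a literal reading the subject is a non-completer. SAP 8.1 describes such subjects as completing 14 days of treatment, which points the other way.

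**Size.** Inputs: 44 per group and 132 in total (SAP 4); planning failure rates of 50% on placebo and 25% in either active group (protocol 8.2).

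- Planned failures: 0.50 × 44 = 22 on placebo; 0.25 × 44 = 11 in each active group; 22 + 11 + 11 = 44 of 132.
- Let f be the share of these failures in which dosing ends permanently and the subject is not withdrawn or lost. The number placed in the wrong row is 44 × f: 0 if f = 0, and 44 if f = 1.
- The documents give no value for f, and several features push it below 1. The SAP failure definition includes high-flow oxygen, non-invasive ventilation and a non-study immune modulator, none of which is a dose-stopping condition in protocol 5.4 or 7.3.2. Withdrawal and loss to follow-up are failures but also genuine non-completion. Failures between Day 15 and Day 28 fall after the SAP's 14-day course has ended.
- Case 4 subjects who do not fail lie outside this count. The documents give no number for them.

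**The case against.** The strongest reply is that nothing important is lost. Much of it stands.

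- **Losses are visible.** A reader might infer that true loss of outcome data is hidden in the Discontinued the study row. The documents do not support that. SAP 7.1 and Table 14.1.1.1 break the row down by reason, and SAP Appendix A uses loss to follow-up as its example of a reason displayed even at a count of zero. Table 14.2.1.1 reports loss to follow-up, consent withdrawal, drug discontinuation before discharge and missing WHO level by arm.
- **Not every intubation or end of course is affected.** A reader might infer that all intubated subjects, and all who finish the course in hospital, become non-completers. Protocol 7.3.2 makes intubation a temporary halt, so that case depends on non-restart. The end-of-course case rests on the literal exemption list alone and is at most a missing phrase.
- **Death is a matter of convention.** Some tables list it as a reason for discontinuation. That is acceptable if stated, but SAP 3 does not state it and SAP 6.4 implies the opposite.
- **The link to the table is inferred.** Neither SAP 7.1 nor Table 14.1.1.1 cites the SAP 3 rule. The source, Listing 16.2.1, has its own completion-status field, and the case report form is not among the documents. The inference is still natural, because SAP 3 is the SAP's only general rule for study completion.
- **The protocol version may differ.** The SAP cites version 5.0 and a 14-day course, while the supplied protocol describes up to 28 days. Protocol 4.4 should be confirmed in the cited version. The conflict between SAP 3 and SAP 6.4 does not depend on this.

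A reader might also infer that a third of the trial will appear as drop-outs, with a significant difference between arms. The 44 is only a ceiling. No test of disposition is planned, and testing those counts would merely restate the assumed efficacy difference.

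**Conclusion.** The concern holds in a limited form. SAP 3 mixes treatment discontinuation with study discontinuation. It is a wrong rule rather than a missing detail, because it contradicts protocol 4.4 and is inconsistent with SAP 6.4. Permanent adverse-event stops and deaths on treatment are the clear cases. Intubation counts if drug is never restarted, and end of course counts only on a literal reading.

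The number affected cannot be determined from the documents. The range of 0 to 44 of 132 assumes the planning failure rates, and the upper end further assumes that every failure ends dosing permanently with nobody withdrawn or lost. The conclusion also assumes that Table 14.1.1.1 follows the SAP 3 rule and that version 5.0 retains protocol 4.4.

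The damage is confined to reporting. The ITT, mITT and safety sets do not use the rule, the per-protocol set has its own completion wording, and the primary Fisher comparison is unchanged. It should be corrected, but it does not threaten the main result.

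**What to change.** - In SAP 3, define study completion by follow-up: clinical and vital status known at Day 56, or death on study. Limit non-completion to withdrawal of consent or loss to follow-up, and delete the treatment-based exception.
- In Table 14.1.1.1 and Listing 16.2.1, report treatment completion and early treatment stop by reason in rows or columns separate from study completion. State there how temporary halts and the end of the 14-day course are classified for reporting.
- State in SAP 7.1 that the table and the completion-status field use the SAP 3 definition.
- Align the completion wording in SAP 6.4, so that one subject cannot be a completer in one row and a non-completer in another.
- Confirm protocol 4.4 in version 5.0.

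The cost is a short change of SAP wording and a few rows in one table and one listing. The SAP already plans to list dosing records, daily WHO level and disposition dates, and its schedule includes Day 28 and Day 56 status, so no new data collection should be needed. The case report form should be checked to confirm this.

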- ¹ PK assessment will be performed for the initial 15 subjects enrolled. Blood (5 ml) will be collected for plasma collection at baseline (pre-treatment), and then at 1, 2, 4, and 8 hr. Trough measurements will be obtained as indicated for all study participants
- ^m The clinical record should be reviewed at Day 28 and Day 56 as relevant to denote date of discharge, date of death, or clinical status (WHO COVID-19 Classification Level); if discharged, subjects should be contacted by telephone to ascertain clinical status.
- ⁿ PBMCs will be collected at specified sites only

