4. DETERMINATION OF SAMPLE SIZE

Based on the initial data obtained to date and data in the literature, it is anticipated that approximately 50% of subjects hospitalized with PCR-positive SARS-CoV-2 infections (WHO COVID-19 Classification level 3 or 4) will experience treatment failure at day 28 from enrollment. Treatment failure is defined as progression to WHO COVID-19 classification level of 6 or greater as defined by one or more of the following: the need for high-flow oxygen or non-invasive ventilation, the need for intubation or mechanical ventilation (level 6), the need for ECMO (level 7), or any cause death (level 8); the initiation of a non-study immune modulator; withdrawing consent from the study; becoming lost to follow-up; or discontinuation of treatment for any reason other than renal function or pregnancy. The sample size estimate for this proof of concept is based on Fisher's Exact two-sided test for 2 proportions using NQuery 8 (www.statsols.com). Estimates of admitted patients requiring salvage therapy is unknown, however, the clinical data set who require intubation is a likely subset of those whose condition worsens but do not progress to respiratory compromise.

Although the interim analysis will utilize masked treatment assignments, the O'Brien Fleming group sequential sample size estimation confirms that a single interim look would retain a cumulative exit probability of 70% with a cumulative alpha =0.05 after the final analysis using the target enrollment of 132 (44 per group) to detect a reduction of those reaching the endpoint of treatment failure. This study is not powered to assess statistically significant differences between GLS-1027 doses. A gate-keeping method will be used to compare the highest dose to placebo first and then compare the lower dose if the higher dose shows significant benefit.

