8. EFFICACY ANALYSES

8.1. Definition of the Primary Efficacy Endpoint

The primary endpoint is treatment failure within 28 days of enrollment. Treatment failure is defined as:

- Progression to WHO classification level 6 or greater including the need for high-flow oxygen or non-invasive ventilation
- Receiving salvage therapy with a non-study immune-modulator (Appendix A).
- Lost to follow-up through hospital transfer, within the 14-day primary treatment period.
- Discontinuation of study drug for any cause prior to day 14 or hospital discharge will be considered as a treatment failure, except for those for whom study drug was temporarily suspended due to a decrease in renal function (creatinine clearance of < 60 mL/min), other reasons for temporary cessation of treatment listed in Section 7.3.2 of the protocol, or for discontinuation in the case of pregnancy. These subjects will be followed for the primary endpoint at 28 days with long-term follow-up at day 56.

Subjects who complete 14 days of treatment but remain hospitalized but do not meet the criteria for treatment failure, will not considered be as treatment failures with respect to the primary endpoint.

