Treatment Failure [1]	x (xx.x%)	x (xx.x%)	x (xx.x%)	
Achieved WHO level >=6	x (xx.x%)	x (xx.x%)	x (xx.x%)	
Lost to follow-up	x (xx.x%)	x (xx.x%)	x (xx.x%)	
Withdrawal of informed consent	x (xx.x%)	x (xx.x%)	x (xx.x%)	
Required salvage therapy	x (xx.x%)	x (xx.x%)	x (xx.x%)	
Discontinued study drug prior to discharge	x (xx.x%)	x (xx.x%)	x (xx.x%)	
Had missing assessment of WHO level classification	x (xx.x%)	x (xx.x%)	x (xx.x%)	
p-value [2]	0.xxxx	0.xxxx	, ,	
Maximum WHO Level = 6 (Intubation or Mechanical Ventilation)	x (xx.x%)	x (xx.x%)	x (xx.x%)	
Maximum WHO Level = 7 (Requirement for ECMO)	x (xx.x%)	x (xx.x%)	x (xx.x%)	
Maximum WHO Level = 8 (Death)	x (xx.x%)	x (xx.x%)	x (xx.x%)	

^[1] Subjects who met any of the reasons listed are considered treatment failures. Subjects who failed treatment for multiple reasons are counted once for each reason.

Reference: Listing 16.2.6.1

Programming note: Repeat for Table 14.2.1.2 Analysis of Overall Treatment Failure (mITT Population).

Programming note: Repeat for Table 14.2.1.3 Analysis of Overall Treatment Failure (PP Population).

Programming note: P-values will not be provided for corticosteroid use/non-use subset pages.

^[2] P-value is calculated using a Fisher's exact test and compares the active treatment to placebo. Will only be provided for the 120 mg group if the 360 mg group is significant.

GeneOne Life Science Inc.

Page 1 of 1

Protocol: GLS27-005

Table 14.2.2.1.1

Summary of the Number of Days Requiring ICU Care
(ITT Population)

	GLS-1027	GLS-1027	Placebo
	120 mg	360 mg	(N=XX)
	(N=XX)	(N=XX)	, ,
umber of Days Requiring ICU Care			
n	X	X	Х
Mean (SD)	xx.xx (xx.xxx)	xx.xx (xx.xxx)	xx.xx (xx.xxx)
Median	x.xx	x.xx	x.xx
nearan			xx.x, xx.x

Reference: Listing xxxxx

Programming note: Repeat for Table 14.2.2.1.2 Summary of the Number of Days Requiring ICU Care (PP Population).

Protocol: GLS27-005

Table 14.2.2.2.1

Summary of the Number of Days on Mechanical Ventilation
(ITT Population)

	GLS-1027	GLS-1027	Placebo
	120 mg	360 mg	(N=XX)
	(N=XX)	(N=XX)	, ,
umber of Days on Mechanical Ventilation			
umber of Days on Mechanical Ventilation n	х	x	×
	x xx.xx (xx.xxx)	x xx.xx (xx.xxx)	x xx.xx (xx.xxx)
n			

Reference: Listing 16.2.6.2

Programming note: Repeat for Table 14.2.2.2.2 Summary of the Number of Days on Mechanical Ventilation (PP Population).

Protocol: GLS27-005

Table 14.2.2.3.1 Summary of the Number of Days Requiring Nasal Oxygen (O_2) Administration (ITT Population)

	GLS-1027	GLS-1027	Placebo

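### SAP 8.1 counts loss to follow-up only through transfer within 14 days and omits consent withdrawal, while SAP 4 and Table 14.2.1.1 count both as primary failure without that limit

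*SAP*

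**What the plan says.** **Failure components in the SAP.** Section 8.1, the operative definition, opens with "The primary endpoint is treatment failure within 28 days of enrollment". It then gives four components: WHO progression, salvage therapy, loss and drug discontinuation. The loss component reads "Lost to follow-up through hospital transfer, within the 14-day primary treatment period". Consent withdrawal is not a component. Stopping drug before Day 14 or discharge is a failure, with stated exceptions.

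Section 4 (sample size) also describes failure at Day 28, but its list includes "withdrawing consent from the study; becoming lost to follow-up", with no condition on transfer or on 14 days.

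Table 14.2.1.1 in Appendix C has failure rows for loss to follow-up (unqualified), for "Withdrawal of informed consent" and for "Had missing assessment of WHO level classification". Its first footnote makes a subject a failure if any listed reason applies. Section 8.3 rules out imputation beyond what is described.

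**Schedule.** SAP Table 1 marks WHO level on Days 1 to 15, 28 and 56. The ICU, nasal oxygen, CPAP, ventilation and ECMO rows stop at Day 15. Footnote m says "The clinical record should be reviewed at Day 28 and Day 56 as relevant to denote date of discharge, date of death", or clinical status as WHO level, with a telephone call for discharged subjects. Section 3 says "Primary outcome will be assessment at day 28". Table 14.2.1.1 reports the maximum WHO level reached.

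**The concern.** Two programmers working from different parts of the same SAP would code the same patient differently on the primary endpoint. The situation is foreseeable: discharged patients are followed by telephone, and some will not answer.

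The stakes extend beyond one p-value. Under the gatekeeping rule in SAP 4 and the second footnote of Table 14.2.1.1, the 120 mg p-value is shown only if the 360 mg comparison is significant. A coding choice in the 360 mg or placebo arm can therefore decide whether the 120 mg dose is tested. Making that choice after unblinding would be hard to defend.

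Separately, a patient who needs high-flow oxygen, non-invasive ventilation, intubation or ECMO after Day 15 and recovers before Day 28 meets the 28-day definition. SAP Table 1 has no scheduled recording that is certain to show it.

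**Working it through.** **1. Same patient, three parts of the SAP.** These are invented patients with no other failure event, and each text is read literally.

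| Patient | SAP 8.1 | SAP 4 | Table 14.2.1.1 |
|---|---|---|---|
| Withdraws consent and stops drug on Day 6, in hospital | Failure (discontinuation) | Failure | Failure |
| Transferred and lost, Day 10 | Failure | Failure | Failure |
| Transferred and lost, Day 20 | Not failure | Failure | Failure |
| Discharged well on Day 8, not reached at Day 28 | Not failure | Failure (loss) | Failure (loss or missing WHO level) |
| Completes 14 days of drug, withdraws on Day 20 | Not failure | Failure | Failure |
| Followed throughout, but a WHO level is missing | Not failure | Not failure | Failure, if the row means any missing level |

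The first two rows agree. The next three are the conflict. The last turns on a row that does not say which assessment, or how many, must be missing.

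**2. Does the supplied protocol settle it?** Only in part, and its version is not shown, whereas the SAP cites version 5.0.
- Synopsis and 8.2: any loss to follow-up and any consent withdrawal are failures.
- 8.6: transfer loss within 28 days is a failure.
- 8.9: transfer loss is a failure in ITT and mITT; withdrawal without endpoint assessment is a failure.
- 4.4: every transfer is a failure. A subject discharged within 28 days who cannot be reached is lost only for 56-day outcomes, and discharge without relapse is a success.

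So withdrawal before assessment has a consistent answer, and transfer loss has a 28-day one. The discharged, unreached patient does not: the synopsis and 8.2 point to failure, 4.4 to success. The 4.4 rule also depends on absence of relapse, which is unknown for someone not reached.

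**3. Schedule against window.** Days 16 to 27 have no scheduled WHO recording: 27 − 16 + 1 = 12 of the 28 endpoint days. Day 28 does have a record review, concomitant medications, adverse events and a WHO level, but no entry for the worst level since Day 15.

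**4. Size.** Inputs are 44 per arm (both documents) and 50% v 25% failure (the 25% is in the protocol only). The plan's 70% power reproduces on these inputs. The drift is 0.25 / √(0.5×0.5/44 + 0.25×0.75/44) = 0.25 / 0.0997 = 2.51. With two-look O'Brien-Fleming bounds 2.797 and 1.977, power is 70.4%. That is a normal approximation; a single-look exact Fisher test gives 61.1%, which is a separate matter.

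The planned rates give 44 × 0.50 = 22 and 44 × 0.25 = 11 failures. Two-sided Fisher exact p (placebo v drug failures, each of 44):

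| Change from 22 v 11 | Counts | p |
|---|---|---|
| None | 22 v 11 | 0.027 |
| One fewer on placebo | 21 v 11 | 0.045 |
| One more on drug | 22 v 12 | 0.048 |
| One more on placebo | 23 v 11 | 0.015 |
| Two fewer on placebo | 20 v 11 | 0.073 |
| Two more on drug | 22 v 13 | 0.081 |
| Two more on placebo | 24 v 11 | 0.0085 |
| One more on placebo, two on drug | 23 v 13 | 0.0503 |
| Proportional fall in both | 20 v 10 | 0.042 |
| One more in each | 23 v 12 | 0.029 |
| Two more in each | 24 v 13 | 0.030 |

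These are fragility examples, not forecasts. The documents give no rate of loss, withdrawal or late transient escalation.

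**The case against.** **Section 8.1 governs.** SAP 4 is a sample-size section, and the unqualified loss row in the table could be shorthand for 8.1. This has force for that one row. It cannot explain the withdrawal and missing-assessment rows, which have no counterpart in 8.1, and the table is what will be programmed.

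**Withdrawal is already covered.** A reader might infer that 8.1 ignores withdrawal altogether. It does not: withdrawal that stops drug before Day 14 or discharge is caught by the discontinuation rule. The gap is later withdrawal.

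**Late events will be lost.** A reader might infer this from Table 1. The documents do not show it. A schedule lists activities, not data fields, and the CRF was not supplied. The SAP cites CRF version 1.05 of February 2021, which predates protocol 5.0 of August 2021. The supplied protocol schedules WHO level and respiratory support daily to Day 29, so a CRF of that age may well carry those days. The listings for WHO level and respiratory support state no Day 15 stop. Intubation or ECMO would often qualify as a serious adverse event. What remains is a question to check.

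**The endpoint is status on Day 28.** The wording in SAP 3 could suggest this, but 8.1, 8.2, 8.3 and the maximum-level rows all describe the whole period.

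**The p-values show only small-sample fragility.** True. No mechanism for imbalance between blinded arms is offered, and recoding can help the drug as well as hurt it. They show why the rule should be fixed in advance, not that the result is biased.

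**Conclusion.** The definition conflict stands, with high confidence, on the SAP text alone. It is confined to loss without transfer, transfer loss on Days 15 to 28, withdrawal after Day 14 or after discharge, and the undefined missing-WHO-level row. The data-capture point stands only as a conditional check, with medium confidence, because the CRF and protocol version 5.0 were not available.

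The size is unknown because no event rate is given. At the planned rates, two patients recoded in one arm are enough to cross 0.05 or to strengthen the result; one patient recoded in one arm is not enough to cross, and neither are the balanced changes tested. Nothing in the documents supports a claim of bias for or against the drug. Differences between the supplied protocol and the SAP may reflect versions and need reconciling; they are not taken as errors. This should be fixed before unblinding.

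**What to change.** 1. In SAP 8.1, give one component list with a time limit for each component, and make SAP 4 and Table 14.2.1.1 match it.
2. Change the transfer-loss window from 14 to 28 days, to match the endpoint.
3. List consent withdrawal before endpoint assessment as a failure, in line with SAP 4, the table and Protocol 8.9.
4. Choose one rule for patients discharged without failure and not reached at Day 28. Reconcile SAP 4 and Protocol 8.2 with Protocol 4.4 rather than adopting either by default, and report the other coding as a sensitivity analysis.
5. Define the missing-assessment row (which assessment, and when) or delete it.
6. Check whether the CRF captures Days 16 to 27. If it does not, use the existing Day 28 record review and call to abstract the worst WHO level since Day 15 and the start and stop dates of respiratory support, and say in 8.1 that the endpoint uses them.

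Items 1 to 5 cost SAP wording, a table shell edit and one extra analysis. Item 6 costs nothing if the fields exist; otherwise it needs a few eCRF fields and some retrospective abstraction for patients already past Day 28. Sample size and visits do not change.
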